8.3.2.2. Abuse, Misuse, or Medication Error

Abuse is the persistent or sporadic, intentional excessive use of the study treatment which is accompanied by harmful physical or psychological effects.

A medication error is any preventable incident that may cause or lead to inappropriate study treatment use or patient harm while the study treatment is in the control of the health care professionals or patients. Such incident may be due to health care professional practice, product labeling, packaging and preparation, procedures for administration, and systems, including the

following: prescribing, order communication, nomenclature, compounding, dispensing, distribution, administration, education, monitoring, and use.

All occurrences of abuse, misuse, or medication error with any study treatment are to be reported on an SAE report form to Karyopharm Pharmacovigilance regardless of whether or not an AE or SAE has occurred due to the abuse, misuse, or medication error. If the abuse, misuse, or medication error is associated with an SAE, the SAE report form must be submitted to Karyopharm Pharmacovigilance within 24 hours of awareness. If there is no AE or SAE, the report must be submitted as soon as possible.

8.3.2.3. Occupational Exposure

Occupational exposure is the exposure to a study treatment as a result of one's professional or non-professional occupation. For this protocol, please follow the instructions for preparation and administration of the bortezomib and dexamethasone.

All occurrences of occupational exposure with any study treatment are to be reported on an SAE report form to Karyopharm Pharmacovigilance regardless of whether or not an AE or SAE has occurred due to the occupational exposure. If the occupational exposure is associated with an SAE, the SAE report form must be submitted to Karyopharm Pharmacovigilance within 24 hours of awareness. If there is no AE or SAE, the report must be submitted as soon as possible.

9. STATISTICAL METHODS

A statistical analysis plan (SAP) will be finalized prior to database lock. Any changes from the statistical analyses described in this document will be described in the SAP, and any deviation from the final SAP will be described in the final report.

9.1. General Considerations

Tabulations will be produced for appropriate disposition, demographic, baseline, efficacy, and safety parameters. For categorical variables, summary tabulations of the number and percentage of patients within each category (with a category for missing data) of the parameter will be presented. For continuous variables, the number of patients, mean, median, standard deviation, minimum, and maximum values will be presented. Time-to-event data will be summarized using Kaplan-Meier methodology with median event time and associated 2 sided 95% confidence intervals, as well as number and percentage of patients with events and censored patients.

Patients who are in Part A or Part B of the Dose Escalation Phase being treated at the RP2D \pm niacin ER dose chosen for expansion will be included in the efficacy and safety assessment of the Dose Expansion Phase.

Efficacy and safety endpoints will be presented separately for Part A, B and two dose levels of Part C.

9.2. Determination of Sample Size

9.2.1. Sample size for Part A and B:

The sample size for the Dose Escalation Phase is based on a standard 3+3 design for the purpose of determining the RP2D and MTD (Part A) and the RP2D and MTD of KPT-9274 co-administered with niacin ER (Part B). Each cohort in Parts A and B of the Escalation Phase will consist of 3 or 6 patients per cohort.

For the Dose Expansion Phase, up to 65 additional patients may be enrolled at the RP2D for KPT-9274 single agent or KPT-9274 + niacin ER (up to 45 patients in the KPT-9274 \pm niacin ER cohort; if Dose Expansion is conducted with KPT-9274 + niacin ER then an optional cohort of up to 20 additional patients in the KPT-9274 single agent cohort).

Assuming that 9 dose levels of KPT-9274 are evaluated during both Part A and Part B of the Dose Escalation Phase and up to 65 additional patients are enrolled in the Dose Expansion Phase, the total combined enrollment is estimated to be 175 patients.

9.2.2. Sample size for Part C:

Two dose levels of KPT-9274 (30 and 40 mg) + nivolumab will be tested. A maximum of 10 patients may be enrolled at each dose level. Additional dose levels (20 mg or 60 mg) might be evaluated if an optimal dose is not identified and the safety review committee is in agreement.

9.3. Analysis Populations

9.3.1. Intent-to-Treat Population

The intent to treat (ITT) population for Part A and Part B will consist of all patients who receive at least one dose of the RP2D \pm niacin ER chosen for expansion. Note that patients who are in the Dose Escalation Phase being treated at the RP2D \pm niacin ER dose will be included.

The ITT population for Part C will consist of all patients who receive at least one dose of study treatment.

ITT population will be used for primary analyses of efficacy.

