Patients must complete a minimum of 1 cycle of treatment, defined as receiving \geq 75% of KPT-9274 doses during Cycle 1 (e.g., \geq 9 of 12 doses in the 3 doses/week schedule), or have a DLT within the first cycle of treatment to be evaluable for dose escalation decisions. Dose escalation decisions will occur when the cohort of patients has met these criteria.

Dose escalation decisions will be made by enrolling Investigators and Karyopharm study personnel. Decisions will be based on an evaluation of all relevant data available from all dose levels evaluated in the ongoing study including safety information, DLTs, all CTCAE (Version 4.03) toxicity data during Cycle 1 and PK data (if available) from evaluable patients (see Section [6.2.6.3](#))

[Table 13](#) describes the starting dose and the dose cohorts that may be evaluated in Part A. A similar dose escalation plan will be used in Part B. To better evaluate the safety, tolerability and PK of KPT-9274, additional cohorts of patients may be enrolled on alternate dosing schedules, at preceding dose levels, or to intermediate dose levels before or while proceeding with further dose escalation.

Dose escalation for Part A and Part B will be conducted as follows:

- If 0 of 3 patients experiences a DLT, escalate to next higher dose cohort.
- If 1 of 3 patients experiences a DLT, that cohort will be expanded to 6 patients. If 1 of 6 patients experiences a DLT, escalate to the next higher dose cohort;
- If \geq 2 of 3 or \geq 2 of 6 patients experience a DLT, MTD is exceeded. If the MTD is exceeded, the patients will be de-escalated to the next lower dose level (the MTD).

Part C (KPT-9274 + nivolumab):

The initial cohort will consist of 3 enrolled patients who will be treated at a dose of 30 mg KPT-9274, co-administered with a dose of 480 mg nivolumab. If these patients do not experience a DLT during Cycle 1, the KPT-9274 dose will be escalated to 40 mg for another cohort of 3 patients upon approval during a dose decision meeting. A maximum of 10 patients may be enrolled at each dose level.

Additional KPT-9274 dose levels (e.g., 20 mg or 60 mg) may be evaluated if an optimal dose is not identified and the safety review committee is in agreement.

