 - Patients may be re-started on KPT-9274 either at the original dose OR at one dose level lower upon recovery to Grade ≤ 1 or baseline (see [Table 15](#) for pre-specified dose modifications for AEs and [Table 16](#) for dose modification guidelines for KPT-9274).

For the Dose Expansion Phase, if an event meeting the definition of a DLT, but without necessarily occurring within the first 28 days, is observed in > 33% of patients at any time, or if > 33% of treated patients have withdrawn consent due to toxicity, enrollment will be held and a meeting with all investigators and Karyopharm/Medical Monitor will take place to review the

events and discuss their clinical significance. Based on this review, the sponsor may elect to reduce the dose for enrolled patients and to resume enrollment of the expansion cohort at this lower dose, or the enrollment into the expansion cohort will be stopped.

[Table 15](#) summarizes the pre-specified dose modifications (i.e., Dose Levels 1 through 5+) for AEs listed in [Table 16](#).

Table 15: Pre-specified Dose Modifications for Adverse Events

Dose Level	KPT-9274 Dose (mg) (Dose Escalation, Part A and Part B)*
5+	Increase in 20 mg increments
4	40 mg
3	30 mg
2	20 mg
1	10 mg

*From the RP2D, patients will be dose reduced by 1 dose level increments as needed as in [Table 16](#).

For dose reduction, find the current dose in [Table 15](#) and reduce as indicated in [Table 16](#).

Table 16: KPT-9274 Dose Modification and Supportive Care Guidelines

Toxicity and Intensity	Dose Modification
Non-hematologic Toxicity	
Grade 1	
Maintain dose.
 
Consider instituting supportive care medications per institutional guidelines. For additional options, see NCCN Clinical Practice Guidelines in Oncology for Fatigue, Palliative Care, and Antiemesis, also refer to Benson guidelines.

Grade 2	
Institute supportive care medications per institutional guidelines. For additional options, see NCCN Clinical Practice Guidelines in Oncology for Fatigue, Palliative Care, and Antiemesis, (also refer to Benson Guidelines).
 
For Grade 2 toxicities, the Investigator should consult with the Karyopharm Medical Monitor when deciding on treatment delays or modifications. If modifications are desired, guidelines for AEs \geq Grade 3 should be followed. At the Investigator's discretion after consulting with the Karyopharm Medical Monitor, patients may continue on KPT-9274 uninterrupted at their current dose.

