9.5. Efficacy Analysis

Disease response will be evaluated according to RECIST 1.1 (advanced solid malignancies) [Appendix 4](#)) or Lugano Classification (NHL) ([Appendix 3](#)) and will include the following endpoints: Time-to-event efficacy endpoints will be performed using the same Kaplan-Meier method for estimation of summary statistics, and will include the 25th, 50th (median) and 75th percentiles, associated two-sided 95% Cis (if estimable), and number of events and censored observations.

- Overall response rate (ORR): The analysis of ORR will be performed by calculating the point estimate of the percentage of patients who have either CR or PR, presented as the number and percentage of patients, including a two-sided 95% CI.
- Duration of response (DOR): the duration of time from first meeting CR or PR measurement criteria (whichever occurs first) until the first date that Progressive Disease (PD) recurrence is objectively documented. Patients without documented PD will be censored on the date of last disease assessment.
- Disease control rate (DCR): The analysis of DCR will be similar to that described for ORR, for patients who achieve CR, PR, or SD for ≥ 16 weeks.
- Duration of disease control: the duration of time from date of first study treatment until the first date the PD is objectively documented. Patients without documented disease progression will be censored on the date of last disease assessment.
- Progression-free survival (PFS): the duration of time from date of first dose of study treatment until the first date that PD is objectively documented or death due to any cause. Patients without documented PD will be censored on the date of last disease assessment.
- Overall survival (OS): the duration of time from date of first dose of study treatment until death from any cause. Patients who withdraw from the study or are alive at the time of data analysis will be censored on the date of last contact.

- TTP: The duration of time from date of first dose of study treatment to date of PD. Patients who withdraw from the study or are alive at the time of data analysis per Section 2.2.2 without documented DD will be censored on the date of last contact.

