Please note that the composition of the expansion groups (e.g., number of patients with NAPRT1 positive vs NAPRT1 deficient tumors) may change based on the results from the escalation phase. An additional, optional KPT-9274 single agent expansion cohort will consist of  $\sim 20$  patients with any tumor mutational status.

Patients in the Dose Expansion Phase may be treated with the RP2D of KPT-9274  $\pm$  niacin ER according to the same schedule administered in the Dose Escalation Phase of the study. Patients who are in Part A or Part B of the Dose Escalation Phase being treated at the RP2D  $\pm$  niacin ER dose chosen for expansion will be included in the efficacy and safety analyses of the Dose Expansion Phase.

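### Read literally, Protocol 9.3.1 builds the RP2D efficacy set on one dose received, not on starting regimen, so patients reduced from higher doses can enter with their earlier follow-up counted

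*Protocol*

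**What the plan says.** - **Entry rule.** Protocol 9.3.1: the Parts A and B population "will consist of all patients who receive at least one dose of the RP2D", with or without niacin ER, chosen for expansion. The next sentence begins "Note that patients who are in the Dose Escalation Phase being treated at the RP2D" and says that these patients are included. The section ends: "ITT population will be used for primary analyses of efficacy".
- **Clock.** Protocol 9.5 defines PFS as "the duration of time from date of first dose of study treatment until the first date that PD is objectively documented" or death. OS and TTP start at the same point.
- **Ways down to a lower dose.** Section 6.2.6.1: "If the MTD is exceeded, the patients will be de-escalated to the next lower dose level (the MTD". Section 6.2.8 lets escalation patients whose drug was held for a lesser toxicity restart "either at the original dose OR at one dose level lower upon recovery", and Table 16 gives one-level reductions for more severe toxicity.
- **Expansion at a changed dose.** After a safety review, 6.2.8 lets the sponsor "reduce the dose for enrolled patients and to resume enrollment of the expansion cohort at this lower dose".
- **SAP.** Section 3.1.1 bases primary efficacy on an mITT of everyone treated in Parts A, B and C. Section 1.7 reports no modification of the protocol's statistical section. Section 1.1 (Dose Expansion Phase) still says that escalation patients treated at the RP2D "will be included in the efficacy and safety analyses of the Dose Expansion Phase".

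**The concern.** Membership turns on something that happens after time zero. A patient who starts at a higher level must stay on treatment long enough to be reduced before counting as an RP2D patient, yet follow-up is counted from the first, higher dose. Survival up to the reduction is therefore certain by selection, and part of any progression-free time may be. A response reached at the higher dose is also credited to the RP2D. Despite its name, the set is not defined by intention to treat.

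Anti-tumour activity at the RP2D is a primary objective of the expansion in both documents. If few patients are treated there, a handful of reduced patients could visibly lift the activity estimate for a dose that did not produce it.

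**Working it through.** The plan gives no PFS rate, power or effect size for this set, so there is no figure of its own to reproduce. The check has two parts.

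**1. Who can enter by reduction?**

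- Under 6.2.8 a patient with a Cycle 1 DLT in escalation must stop KPT-9274, so these patients cannot enter this way.
- If the RP2D equals the MTD, the level above stopped with at least 2 DLTs in 3 or in 6 patients. That leaves at most 3 − 2 = 1 or 6 − 2 = 4 patients per part who could move down.
- If the RP2D lies below the MTD, patients reduced from cleared levels can add to this.
- Reductions without a DLT are foreseeable. Table 11 shows treatment-related Grade 3 anaemia in 22 of 47 patients, Table 14 lists only Grade 4 anaemia as a DLT, and Table 16 names a one-level reduction among the options for Grade 3 or higher.

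**2. How much time is built in?**

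Scheduled scans start at week 8 ± 7 days (Protocol 7.3.2.1 and 7.3.3.1). Protocol 5.2 requires removal at documented progression, so a patient reduced after a clean first scan had no documented progression by then. A patient reduced earlier is known only to be alive and not taken off for clinical progression. Under the model below, such a patient's 16-week rate stays near the true rate.

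Assumptions, not document figures: exponential PFS with median m weeks, and reduction at w = 8, just after a clean scan.

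- Assigned patients: S = exp(−ln 2 × 16/m)
- Reduced patients: Sr = exp(−ln 2 × (16 − 8)/m)
- Mixed set: (na × S + nr × Sr)/(na + nr)

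For m = 8: S = 0.250 and Sr = 0.500.

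- 6 assigned + 4 reduced: (6 × 0.250 + 4 × 0.500)/10 = 0.350
- 6 assigned + 1 reduced: (6 × 0.250 + 0.500)/7 = 0.286
- 45 assigned + 4 reduced: (45 × 0.250 + 4 × 0.500)/49 = 0.270

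| Assumed median (weeks) | True 16-week rate | Reduced patients | 6 + 4 | 45 + 4 |
|---|---|---|---|---|
| 8 | 0.250 | 0.500 | 0.350 | 0.270 |
| 12 | 0.397 | 0.630 | 0.490 | 0.416 |
| 16 | 0.500 | 0.707 | 0.583 | 0.517 |

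For m = 8 the mixed median beyond week 8 solves exp(−ln 2 × t/8) × (na + 2nr)/(na + nr) = 0.5. This gives 11.9 weeks for 6 + 4 and 8.9 weeks for 45 + 4, against a true 8. Under the same formula a later reduction carries more built-in time.

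**Contingent points**

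- *Schedule.* Section 9.3.1 names a dose only, and the expansion objective in 2.1.1 lists the RP2D and its schedule(s) separately. Table 10 has 7 patients at 40 mg qodx3 and 5 at 40 mg qodx2. If 40 mg single agent became the RP2D, those 5 of 12 (42%), on 2 × 40 = 80 mg per week instead of 3 × 40 = 120 mg, are not clearly excluded.
- *Changed expansion dose.* If expansion resumes at a lower dose, 9.3.1 does not say whether the later patients belong.
- *Niacin.* Section 6.9.1 allows niacin ER to be added after Cycle 1, so receipt also leaves a patient's niacin group open.

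**The case against.** The strongest reply is that the SAP is the later document and its mITT has no RP2D condition. Protocol section 9 allows the SAP to describe changes. This stands for the SAP's primary efficacy analysis, but it does not close the point. SAP 1.7 denies any change, the mITT covers every dose level and gives no set for activity at the RP2D, and SAP 1.1 keeps the undefined group in the expansion analyses.

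Second, the wording about escalation patients being treated at the RP2D is naturally read as the cohort enrolled at that level. That reading is fair and probably intended. The first sentence of 9.3.1 is broader, however, and nothing limits it.

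Third, efficacy here is descriptive, and the main expansion is about 45 patients. Both are true, and they limit the consequence.

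A reader might go further and infer three things that the documents do not support:

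- *Every reduced patient brings guaranteed progression-free time.* No scheduled scan precedes week 8, and de-escalation of a stopped cohort follows Cycle 1 DLTs, so it may well come before that scan. SAP 1.5 also allows treatment past progression where there is clinical benefit. That conflicts with Protocol 5.2, and the two passages must be reconciled. Under the SAP text only survival to the reduction is certain.
- *The futility rule in 9.5.1 has the same gap.* It counts patients enrolled under the 3+3 design and enrols more if needed to reach ten, which points to enrolment at the level.
- *Schedules will be mixed, or expansion patients dropped.* Each needs a condition that has not been met. No RP2D is declared, and a lowered dose could simply become the one chosen for expansion.

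**Conclusion.** The point holds as a defect of definition. Taken literally, Protocol 9.3.1 lets a later dose change decide who is in the primary efficacy set while the clock starts at a different dose, and the SAP does not supply a clean alternative for the expansion objective.

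The size depends on the number of patients. With assumed medians of 8 to 16 weeks and entry just after a clean week-8 scan, 4 reduced patients among 10 raise the 16-week progression-free rate by about 8 to 10 points. Four is the most that a stopped six-patient cohort can supply. The same 4 joining 45 raise it by no more than about 2 points. Reductions before the first scan add less than the model shows. The bias therefore matters mainly if the RP2D set stays small. The schedule and changed-dose points are ambiguities to close, not errors already present.

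**What to change.** Define the RP2D efficacy set as all patients whose assigned regimen at C1D1 (dose, schedule, with or without niacin ER) is the RP2D regimen chosen for expansion, plus all patients enrolled in the expansion, analysed by starting regimen. Patients reduced to that dose stay in their starting cohort.

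- Use this wording in Protocol 9.1, 9.3.1 and 9.5.1 and in SAP 1.1. In 9.5.1 it is for consistency.
- Add the set to SAP 3.1.1 for the expansion objective, beside the mITT.
- Record the change of primary efficacy population in SAP 1.7.

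The cost is wording only: no new data, patients or clinical rule. The set may lose a few patients, and that loss falls hardest where it is small.

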9.3.2. Per Protocol Population

The per-protocol (PP) population will consist of all ITT patients who have received at least 2 cycles of study treatment, are compliant with study assessments, have received at least 80% of their prescribed study medication, and have no major protocol violations that would compromise the assessment of efficacy. Major violations will be determined independently of knowledge of response to therapy, and prior to database lock and study analysis. This population will be used for supportive inferences concerning efficacy, however, if there are major differences between the results in this population and those obtained in the mITT population, this will be taken into consideration in the assessment of efficacy.

9.3.3. Safety Population

All patients who receive any amount of the study treatment will be included in the safety population for analysis. All safety analyses will be performed on the safety population.

9.3.4. Pharmacokinetic Population

All subjects who received at least 1 dose of study medication and had adequate sampling will be included in the PK population. All PK analyses will be performed on the PK population.

9.3.5. DLT Evaluable Population

All patients who complete a minimum of 1 cycle of treatment, defined as having received $\geq 75\%$ of KPT-9274 doses during Cycle 1 (e.g., ≥ 9 of 12 doses in the 3 doses/week schedule), or who have a DLT within the first cycle of treatment, will be included in the DLT evaluable population.

9.4. Data Analysis and Presentation

Summary tabulations will be provided for disposition, demographic, baseline, efficacy, PK, and safety data as noted in the following sections. All data collected on the eCRF will be provided in by-patient data listings.

9.4.1. Disposition of Patients

A tabulation of patient disposition will be presented including the number in each analysis population, the number lost to follow-up, the number that withdrew, and reason(s) for withdrawal.

9.4.2. Demographic Characteristics

Demographic characteristics will be summarized by dose cohort, as well as overall, and will include date of birth, sex, race, ethnicity, and age at time of consent. For sex, race, and ethnicity, the summary statistics will be the number and percentage of patients within each category. The categories for race will be those recorded in the database. For age at time of consent, the mean, median, minimum, maximum, and standard deviation will be provided for each arm and the total sample. No formal hypothesis testing of differences among dose cohorts will be performed.

